**Table 1-2: Additional study assessments**

Assessment	When applicable
For study participants who experience infusion reactions (excluding local injection site reactions):	
Complement and cytokines	In study participants who experience an infusion reaction within the first 4 hours after dosing, a sample should be taken at 4 and 8 hours post event. Additionally, sampling is taken in case of a suspected hypersensitivity event or any clinical indication of an unexpected immune response.
For study participants who experience an AE of special monitoring, including severe headache, moderate to severe diarrhea, moderate to severe abdominal pain, or moderate to severe vomiting: If the AE is initially reported during a telephone call, the study participant should be reviewed at the study site as soon as is practically possible for further investigation.	
Complement and cytokines/Exploratory biomarkers	In study participants who experience an AE of special monitoring (as defined in Section 8.3.6 ) within the first 4 hours after dosing, a sample should be taken at 4 and 8 hours post event.
For study participants who experience severe and/or serious headache, the following should be conducted:	
Headache Questionnaire	In study participants who report severe and/or serious headache, this assessment should be performed daily until resolution (ie, if headache becomes moderate or mild, normal collection of AEs should apply) (see Section 8.3.7.1 ). The Headache Questionnaire may be repeated if clinically indicated and at the discretion of the investigator.
Full neurological examination	In study participants who report severe and/or serious headache, a full neurological examination (including fundoscopy) should be performed (see Section 8.3.7.1.2 ). This assessment should include general appearance (including posture, motor activity, vital signs, and meningeal signs, if indicated), cranial nerves, motor system (including muscle tone/power and sensory system), reflexes (including deep tendon reflexes), coordination (gait, if possible), and fundoscopy. The neurological assessment may be repeated if headache continues and it is clinically indicated and at the discretion of the investigator.
CT scan and lumbar puncture for CSF collection	In study participants who report severe and/or serious headache, other diagnostic procedures including a CT scan (if indicated, and at the discretion of the investigator) and lumbar puncture for CSF collection (if clinically indicated, and at the discretion of the investigator) should be performed (see Section 8.3.7.1.3 and Section 8.3.7.1.4 , respectively).

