- r Applicable only to participants experiencing severe and/or serious headache(s). The Headache Questionnaire will be performed daily until resolution (ie, if headache becomes moderate or mild, normal collection of AEs should apply). Headache Questionnaire should be assessed after Day 5 (at the investigator's discretion) if participants are kept longer in the unit for severe headache.
- s A neurological assessment is to be performed by the investigator or designee for those participants who experience severe and/or serious headaches with a frequency as clinically indicated. This assessment will include:
- 1) General appearance, including posture, motor activity, vital signs, and meningeal signs, if indicated;
  - 2) Cranial nerves;
  - 3) Motor system, including muscle tone and power and sensory system – light touch;
  - 4) Reflexes, including deep tendon reflexes;
  - 5) Coordination, gait (if possible);
  - 6) Fundoscopy.
- The neurological assessment may be performed after Day 5 (to the investigator's discretion) if headache continues. The neurological assessment may be repeated if headache continues and it is clinically indicated and at the discretion of the investigator. In study participants who report severe headache, other diagnostic procedures including a CT scan (if indicated, and at the discretion of the investigator) and lumbar puncture for CSF collection (if clinically indicated, and at the discretion of the investigator) should be performed (see Section 8.3.7.1.3 and Section 8.3.7.1.4, respectively).
- t Complement and cytokine sampling taken predose for all participants and at 4 and 8 hours post event only if an infusion reaction or AE of special monitoring is observed. Backup samples could be stored for later biomarker analyses (up to 20 years).
- u Anti-rozanolixizumab antibodies will be assessed predose and on Days 10, 16, 22, and 57.

In addition to those detailed in [Table 1-1](#), the assessments in [Table 1-2](#) may be required in case of infusion reactions or adverse events (AEs) of special monitoring (severe headache, severe gastrointestinal disorders [eg, diarrhea, abdominal pain, vomiting]). Note that additional vital sign measurements may be taken based on the timing of the assessments.

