### **8.3.6 Adverse events of special interest**

An AE of special interest is any AE that a regulatory authority has mandated be reported on an expedited basis, regardless of the seriousness, expectedness, or relatedness of the AE to the administration of a UCB product/compound. For rozanolixizumab, the following events require immediate reporting (within 24 hours regardless of seriousness) to UCB:

- Potential Hy's Law, defined as  $\geq 3 \times \text{ULN}$  ALT or AST with coexisting  $\geq 2 \times \text{ULN}$  total bilirubin in the absence of  $\geq 2 \times \text{ULN}$  ALP, with no alternative explanation for the biochemical abnormality, must ALWAYS be reported to UCB as an AE of special interest (ie, without waiting for any additional etiologic investigations to have been concluded). Follow-up information should then be reported if an alternative etiology is identified during investigation and monitoring of the participant.

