## 8.9 Biomarkers

Details on processes for collection and shipment and destruction of these samples can be found in the Laboratory Manual.

Serum complement (C3, C4), cytokines, and plasma complement (C3a, C5a) are to be taken pre-dose for all participants and at 4 and 8 hours post event, only if an infusion reaction or AE of special monitoring is observed.

Remaining backup samples could be stored at -80°C for up to 20 years for later exploratory analyses.

Detailed information on sample analyses will be provided in a bioanalytical report.

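### The protocol's rules for post-event complement and cytokine sampling conflict on the definition of the event, the gastrointestinal severity and the hypersensitivity trigger

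*Protocol*

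**What the plan says.** Complement (C3, C4, C3a, C5a) and cytokines are an other-safety endpoint in Protocol Table 3-1. Table 1-1 schedules one sample, predose. Every later sample depends on an event trigger, which the protocol states in four places:

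- **Table 1-1 footnote t:** "at 4 and 8 hours post event only if an infusion reaction or AE of special monitoring is observed".
- **Section 8.9:** the same rule, again "only if an infusion reaction or AE of special monitoring is observed".
- **Table 1-2:** one row covers infusion reactions and adds sampling for suspected hypersensitivity or signs of an unexpected immune response. A second row begins "In study participants who experience an AE of special monitoring (as defined in" and cites Section 8.3.6. It continues "within the first 4 hours after dosing, a sample should be taken at 4 and 8 hours post event". The heading above that row describes an "AE of special monitoring, including severe headache, moderate to severe diarrhea, moderate to severe abdominal pain, or moderate to severe vomiting".
- **Appendix 2 footnote d:** infusion reactions with onset in the first 4 hours, plus the hypersensitivity clause. AEs of special monitoring are not mentioned.

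On the definition, Section 8.3.6 opens "An AE of special interest is any AE that a regulatory authority has mandated be reported on an expedited basis" and lists only potential Hy's Law. AEs of special monitoring are in Section 8.3.7: severe headache, severe gastrointestinal disturbance and opportunistic infection. The sentence in Section 1.3 that introduces Table 1-2 also says severe: "special monitoring (severe headache, severe gastrointestinal disorders [eg, diarrhea, abdominal pain, vomiting". SAP 6.1.7 repeats the severe-only list.

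On stool, Table 1-2, Section 8.3.7.2 and Appendix 2 footnote b call for a sample in moderate or severe diarrhea, with no condition on causality. Section 8.3.7.2.1, which Table 1-2 cites, words the trigger as a severe gastrointestinal AE judged related to the IMP.

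**The concern.** The four statements are meant to be one rule: Amendment 2's summary of changes treats Table 1-1, Table 1-2, Section 8.9 and footnote d as a single edit. As they stand, whether a participant with a moderate gastrointestinal event or a suspected hypersensitivity reaction gives post-event samples depends on which page the site follows.

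The samples are tied to 4 and 8 hours after the event, so a sample not taken then cannot be obtained afterwards. With only a predose sample scheduled, these are the only post-dose complement and cytokine data the study will have. Section 2.3 names gastrointestinal disturbance, headache, and infusion and hypersensitivity reactions among the anticipated effects. Section 4.1 says that manual push is new for this drug and will probably run at higher infusion rates than before.

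**Working it through.** No arithmetic applies. The check sets the current passages side by side.

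| Place | Infusion reaction | AE of special monitoring | Suspected hypersensitivity | Onset window |
|---|---|---|---|---|
| Table 1-1 footnote t | yes | yes | excluded by the restrictive wording | none |
| Section 8.9 | yes | yes | excluded by the restrictive wording | none |
| Table 1-2 | yes | yes, citing 8.3.6 | yes | 4 hours |
| Appendix 2 footnote d | yes | not mentioned | yes | 4 hours |

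**Step 1: the cross-reference.** Followed literally, the special-monitoring row of Table 1-2 applies to potential Hy's Law and to no headache or gastrointestinal event. That cannot be intended, given the heading above it. The reference should be to 8.3.7.

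**Step 2: the gastrointestinal threshold.** Correcting the reference does not finish the job. Section 8.3.7 says severe, so the corrected row would say severe under a heading that says moderate to severe. Of the four places, only Table 1-2 states a gastrointestinal severity. Footnote t and Section 8.9 use the bare term, so they take their threshold from whichever definition the reader adopts: 8.3.7, the lead-in and SAP 6.1.7 give severe, and the Table 1-2 heading gives moderate to severe.

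**Step 3: hypersensitivity.** Take a suspected hypersensitivity event that is not classed as an infusion reaction. Table 1-2 and footnote d call for a sample. Footnote t and Section 8.9 limit sampling to two named triggers, and this is neither. Here one text asks for what the other rules out.

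**Step 4: differences that need aligning but are not direct collisions.**
- Table 1-2 and footnote d state a 4-hour onset window; footnote t and Section 8.9 have none.
- Footnote d leaves out AEs of special monitoring.
- Section 8.3.7.2.1 is narrower on severity and causality than the other three protocol passages on stool, and it refers to gastrointestinal disturbance in general rather than to diarrhea.

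**Step 5: reach into the analysis.** SAP 5.5.1 plans only a listing of complement and cytokine data, and SAP 6.1.7 only a listing of stool results. Counts of AEs of special monitoring follow the SAP's own severe-only definition. None of these changes with the sampling trigger.

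**The case against.** The best defence is that most of these differences can be reconciled.

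- **The window.** Section 1.3 introduces Table 1-2 as adding to Table 1-1, so its 4-hour window does not cancel footnote t. A reader might infer that a severe headache 10 hours after dosing would go unsampled. The documents do not support that: footnote t and Section 8.9 still call for the sample. This stands, and the window is an alignment point only.
- **On-site review.** A reader might also infer a conflict over bringing participants in: "If the AE is initially reported during a telephone call, the study participant should be reviewed at the study site". That instruction appears once, under the heading that includes moderate events, and nothing contradicts it. This stands.
- **Stool.** Section 8.3.7.2.1 says when stool is collected; it does not forbid collection otherwise, and three protocol passages require it for moderate diarrhea. Reading it as a prohibition goes too far.
- **Severity.** Section 8.3.7 can be read as a list for immediate reporting rather than a full definition, and its own subsection 8.3.7.2 is about moderate or severe diarrhea. This is a fair reading. It supports separating the sampling trigger from the reporting list, which the protocol does not do. Section 2.2 applies the label to four UP0060 events, all moderate, but that study's definition is not in the documents, so it settles nothing.
- **Footnote d.** It repeats the infusion-reaction row of Table 1-2, so it looks like an incomplete copy rather than a rival rule. Agreed; it still needs completing.
- **Hypersensitivity.** The Table 1-2 clause sits under the infusion-reaction heading and might be read as part of that category. Its wording presents it as an addition, and footnote d repeats it without that heading, so a separate trigger is the better reading.
- **Discretion.** Appendix 2 lets the investigator order additional tests at any time, and Appendix 3 provides for supplemental measurements. That helps an alert investigator, but it does not make the written rule consistent.

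**Conclusion.** The concern holds as an inconsistency in operative safety instructions. Three faults are real conflicts in current text: the reference to 8.3.6, the gastrointestinal threshold in the Table 1-2 heading, and the exclusion of the hypersensitivity trigger in footnote t and Section 8.9. The 4-hour window, the gap in footnote d and the stool wording are alignment points.

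The size is limited to which safety samples are taken at the site. A reader might infer that the primary endpoint or the safety counts are at risk. They are not: the incidence of TEAEs, the 24-hour reporting rule in 8.3.7 and the SAP analyses do not depend on these triggers. The number of participants affected cannot be estimated from the documents, and no rate is offered. The change should be made because a missed timed sample cannot be recovered and the correction is cheap.

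This rests on two assumptions: that the four places are meant to state one rule, and that the Laboratory Manual, which is not among the documents, does not already settle it.

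**What to change.** 1. In the Table 1-2 special-monitoring row, change the reference from 8.3.6 to 8.3.7.
2. State one trigger, in the same words, in Table 1-2, Table 1-1 footnote t, Section 8.9 and Appendix 2 footnote d: an infusion reaction, an AE of special monitoring, or suspected hypersensitivity or an unexpected immune response, with no 4-hour onset limit.
3. State moderate to severe diarrhea, abdominal pain and vomiting as a sampling trigger separate from the severe-only reporting list in 8.3.7. That keeps the Table 1-2 heading's intent and leaves the reporting rule and the SAP definition alone.
4. In 8.3.7.2.1, change the stool trigger to moderate or severe diarrhea regardless of relatedness.
5. Check that the Laboratory Manual says the same.

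The cost is wording edits and a few extra samples, with no change to the SAP. For events that begin after discharge, the 4- and 8-hour time points may be hard to meet. That is already so under footnote t and Section 8.9, which have no window.

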**Table 1-2: Additional study assessments**

Assessment	When applicable
For study participants who experience moderate or severe diarrhea, stool should be collected:	
Stool sample assessment	In study participants who report moderate or severe diarrhea, stool collection and analysis should be performed (1 sample per episode of diarrhea). The frequency of stool sampling should be as clinically indicated in the opinion of the investigator. Analysis of stool samples will be performed locally (see Section 8.3.7.2.1).

AE=adverse event; CSF=cerebrospinal fluid; CT=computed tomography

## 2 INTRODUCTION

Rozanolixizumab is a humanized IgG4 monoclonal antibody that is being developed as an inhibitor of the activity of the neonatal Fc receptor (FcRn) for IgG.

By blocking the activity of FcRn, rozanolixizumab accelerates the catabolism of IgG antibodies, including IgG autoantibodies. The aim is to reduce the concentration of pathogenic IgG in patients with autoimmune diseases mediated by the action of IgG autoantibodies.

The FcRn recycles IgG and albumin and transports it bidirectionally across epithelial barriers. Multiple studies have shown that FcRn rescues both IgG and albumin from intracellular lysosomal degradation by recycling it from the sorting endosome to the cell surface (Roopenian and Akilesh, 2007). The FcRn may also mediate transcytosis of IgG to facilitate its distribution within tissues. Rozanolixizumab has been specifically designed to block IgG binding to FcRn without blocking the binding and recycling of albumin.

Rozanolixizumab binds with high affinity to FcRn at both neutral and acidic pH. Immunoglobulin G that is constitutively taken up by pinocytosis into cells fails to bind to FcRn, even at the acidic pH found in the endosome. Therefore, it is not recycled and is trafficked to the lysosomes for degradation.

Production of pathogenic IgG autoantibodies is the major pathophysiology leading to a number of autoimmune diseases, which include myasthenia gravis (MG), pemphigus vulgaris, immune thrombocytopenia (ITP), Goodpasture's syndrome, neuromyelitis optica, Guillain-Barré Syndrome, and chronic inflammatory demyelinating polyradiculoneuropathy (CIDP).

As individual disease entities, IgG autoantibody-mediated conditions are relatively rare. Treatment of these disorders remains a difficult clinical problem, with many of these conditions requiring the long-term use of corticosteroids alone or combined with cytotoxic agents. These therapeutic approaches are not effective in all patients and conditions and have broad immunosuppressive effects, which cause considerable toxicity and treatment-related morbidity.

Treatments aimed at reducing the quantity of circulating IgG autoantibodies, including plasmapheresis, immunoadsorption, or high-dose intravenous immunoglobulin, are being used for primary and secondary therapy of autoimmune disease, particularly where corticosteroid-based immune suppression is not or no longer effective (eg, ITP, MG, Guillain-Barré Syndrome, pemphigus vulgaris). The therapeutic approach of these treatments is thought in part to be based on lowering levels of pathogenic autoantibodies, which represents rational and effective treatment modalities of autoimmune diseases.

Therefore, specific removal of the IgG autoantibodies by FcRn blockade may provide an effective therapeutic option for IgG autoantibody-mediated autoimmune disorders.

More detailed information regarding the nonclinical and clinical development programs for rozanolixizumab, including all completed and ongoing studies, can be found in the latest version of the Investigator's Brochure (IB).

For chronic diseases requiring long-term or life-long therapies, alternate modes of subcutaneous (SC) dosing broaden patient options for ease of use and flexibility in how they conduct their drug self-administration. The manual push (MP) technique is a well-established mode of self-administration of SC IgG, which offers the advantages of independence from a syringe driver, reduced infusion times, and reduced material costs. The current study aims to generate and characterize the safety, tolerability, PK, and PD profile for the MP technique compared with the currently used programmable syringe driver, for the SC dosing of rozanolixizumab in healthy participants.

The MP method for SC injection of rozanolixizumab appears to be feasible because the injection volumes of SC rozanolixizumab administered in the clinical program are typically smaller than for SC IgG products (██████████ [HIZENTRA, GAMMANORM]), and the formulation viscosities are comparable (12.0mPa.s vs 14.7mPa.s for Hizentra [Maeder, 2011] and 8.7mPa.s for Gammanorm [Gardulf, 2016]).

The MP technique involves the manual syringing of an investigational medicinal product (IMP) SC with a butterfly needle (eg, 23-25G) (Jolles, 2013). A retrospective analysis of 104 patients self-administering SC IgG found that for push administration using a syringe, volumes of

██████████ (Shapiro, 2010). More than 80% of patients using the MP technique used only 1 infusion site per session, with ██████ as the most common (67.3% of patients) total volume infused. In particular in the pediatric population, MP was preferred in the patient groups of <2 years of age and >10 years of age and has been shown to be a safe and convenient alternative to the pump infusion in children with primary immune deficiency (Shapiro, 2013). Recently, another comparative study switching patients from intravenous IgG infusions to SC IgG infusions demonstrated that the manual push method was similar in tolerability and safety profile (Milota et al, 2019).

## 2.1 Study rationale

For chronic diseases requiring long-term or life-long therapies, alternate modes of SC dosing broaden patient options for ease of use and flexibility in how they conduct their drug self-administration. The MP technique (also referred to as "rapid push") is a well-established mode of self-administration of SC IgG, which offers the advantages of independence from constant use of a syringe driver, reduced infusion times (median ██████████ for abdominal sites), and reduced material costs (Bienvenu et al, 2018). Currently, SC administration of rozanolixizumab occurs via programmable syringe drivers at a targeted ██████████. To enable an alternative to SC dosing via a syringe driver, there is considerable clinical interest in the possibility of employing the MP method for rozanolixizumab, particularly in light of the relatively low volumes involved in rozanolixizumab therapy. The current study aims to generate and characterize the safety, tolerability, PK, and PD profile, including between-participant

variability, for the MP technique compared with the currently used programmable syringe driver, for the SC dosing of rozanolixizumab in healthy participants.

## 2.2 Background

Clinical experience with rozanolixizumab is as follows: a completed first-in-human study in healthy participants (UP0018), a completed Phase 2 study in MG (MG0002), a completed Phase 2 study (TP0001) and ongoing Phase 3 studies (TP0003, TP0006, and TP0004) in primary ITP, a completed Phase 1 study in healthy Japanese, Chinese, and Caucasian participants (UP0060), ongoing Phase 3 studies in MG (MG0003, MG0004, and MG0007), and ongoing Phase 2 studies in CIDP (CIDP01/CIDP04). All clinical dosing of rozanolixizumab has been via the SC route using a syringe driver, except for the evaluation of several escalating intravenous doses in UP0018.

In UP0018, a Phase 1 study in Caucasian healthy study participants, rozanolixizumab was tolerated with an acceptable safety profile after [REDACTED] administration of up to [REDACTED] intravenous and [REDACTED] SC doses. The most frequently reported treatment-emergent adverse events (TEAEs) considered related to IMP per investigator in the rozanolixizumab total SC group were headache (27.8%) and diarrhea (16.7%). Consistent with rozanolixizumab's mechanism of action, plasma IgG concentrations in UP0018 were found to decrease in a dose-dependent fashion, with a maximum percentage change from Baseline of [REDACTED] for [REDACTED] SC, respectively. Following SC dosing in UP0018, no plasma samples had detectable rozanolixizumab concentrations at a dose of [REDACTED] and only 2 study participants had detectable concentrations at [REDACTED]. The only calculable maximum and total rozanolixizumab exposures by the SC route were for the [REDACTED] dose (maximum plasma concentration [ $C_{max}$ ]: 12.41 µg/mL and area under the concentration-time curve from 0 to time t [ $AUC_{(0-t)}$ ]: 643.3h\*µg/mL). As no [REDACTED] dose is planned in UP0106 participants, information regarding redosing at the same infusion site is not necessary.

In UP0060, [REDACTED]-dose SC administration of rozanolixizumab to healthy Japanese, Chinese, and Caucasian study participants was generally well tolerated with an acceptable safety profile after [REDACTED] SC administration of [REDACTED] doses. Overall, patterns in the incidence of TEAEs observed in Japanese and Chinese study participants were generally comparable to those observed in Caucasian participants. In all study participants, a numerically higher incidence of TEAEs was reported for study participants receiving rozanolixizumab (38 participants [77.6%] reported 115 TEAEs) compared with placebo (10 participants [62.5%] reported 23 TEAEs). Among participants receiving rozanolixizumab, there was a trend towards increased incidence of TEAEs with higher doses (55.6%, 75.0%, and 90.0% of participants in the rozanolixizumab [REDACTED] dose groups, respectively). Three participants (6.1%) reported 4 TEAEs of special monitoring (diarrhea [2 events], abdominal pain [1 event], and vomiting [1 event]) in the [REDACTED] cohort, all of moderate intensity. The [REDACTED] dose was concluded by the investigator to be not well tolerated by 1 Caucasian volunteer who reported moderate headache. Dose-dependent reductions in IgG and IgG subclasses, similar to that observed in UP0018, were seen following administration of rozanolixizumab in all 3 ethnicities. Tetanus- and influenza A virus-specific IgG concentrations over time were similar to total IgG following the administration of rozanolixizumab, generally reaching the lowest levels around Day 10 and returning close to Baseline by Day 57; the geometric mean concentrations for tetanus- and influenza A virus-specific antibodies generally remained at acceptable levels for

protection time in all ethnic and dose groups. Overall, the mean value of albumin remained within the normal range over time, and no clinically relevant changes from Baseline were observed. All injection site reactions observed for rozanolixizumab were self-limiting, short-term, and of mild intensity.

